9.7.7. Overall Survival and Time to Next Treatment

OS and TTNT/D will be assessed using unadjusted Kaplan-Meier methods. The median time to event in months will be reported along with the IQR. The 95% CIs for the median time to event will be calculated using log-log transformation. Results will be depicted graphically by Kaplan-Meier curves, and the percentage of patients who reached the outcome and censored patients will also be reported.

OS will be assessed as the time in months from index date to date of death. Patients without an event will be censored at the earliest of the end of continuous closed-claim coverage or the end of data.

TTNT/D will be assessed as the time in months from index date until switch a new treatment or death. Patients without an event will be censored at the earliest of the end of continuous closed-claim coverage, or the end of data.

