9.2. Setting

This study will evaluate adult patients with RRMM who initiate elranatamab. Patients will enter (i.e., index) on the first observed elranatamab claim between 14 August 2023 and the end of data (defined as the latest data at the time of the specified analysis). Limited eligibility criteria will be applied.

Study Period: Start of data availability (01 January 2016) to the end of data

MM diagnosis window: Start of data availability (01 January 2016) to index date

Index date: First elranatamab claim after initial MM diagnosis

Observability: At least 180 days of continuous closed-claims medical and pharmacy enrollment prior to index (inclusive)

[figure not shown]
Baseline period for MM-related treatments and MM-related comorbidities: MM diagnosis to one day prior to index date (unless otherwise specified)

CCI and baseline HCRU assessment window: 180 days prior to index date to index date.

Follow-up: Index date until death, the earliest of the end of data, or end of continuous enrollment (unless otherwise noted). Alternative censoring criteria will be applied for certain outcomes (such as OS, TTD, and TTNT/D); see [Section 9.7](#) for more details.

Figure 1 reflects the time periods of interest in the study cohort.

Figure 1. Study Schematic for Patients Receiving Elranatamab

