3	TTD	Time in months from first administration until last administration prior to treatment discontinuation (continuous). Treatment discontinuation is defined as an 8-week gap in elranatamab (or for the exploratory analysis, teclistamab therapy), next treatment after index treatment (CAR-T, BsABs, bendamustine or belantamab), or death.	Index date to the end of follow-up. Follow-up will be defined based on the censoring criteria described in Section 9.7.4
Health care resource utilization and costs			
4	All-cause IP visits	Medical claim for IP (non-ED) visit (dichotomous)	180 days prior to index date to 1 day prior to index date
		Number of IP (non-ED) visits (continuous)	Step-Up Dosing Period Index date to end of follow-up. Follow-up will be defined two ways to account for gaps in elranatamab use. See Section 9.7.5 for censoring criteria
4	IP visits from the IP table	Medical claim for IP (non-ED) visit sourced from the IP table (dichotomous)	180 days prior to index date to 1 day prior to index date
		Number of IP (non-ED) visits sourced from the IP table (continuous)	Step-Up Dosing Period Index date to end of follow-up. Follow-up will be defined two ways to account for gaps in elranatamab use. See Section 9.7.5 for censoring criteria
4	IP visits from the Non-IP table	Medical claim for IP (non-ED) visit sourced from the Non-IP table where place of service indicates an IP setting (dichotomous)	180 days prior to index date to 1 day prior to index date

		Number of IP (non-ED) visits sourced from the IP table place of service indicates an IP setting (continuous)	Step-Up Dosing Period Index date to end of follow-up. Follow-up will be defined two ways to account for gaps in elranatamab use. See Section 9.7.5 for censoring criteria
4	All-cause OP visits	Medical claim for non-IP/non-ED visit (dichotomous)	180 days prior to index date to 1 day prior to index date
		Number of non-IP/non-ED visits (continuous)	Step-Up Dosing Period Index date to end of follow-up. Follow-up will be defined two ways to account for gaps in elranatamab use. See Section 9.7.5 for censoring criteria
4	All-cause ED visits	Medical claim for ED visit (dichotomous)	180 days prior to index date to 1 day prior to index date
		Number of ED visits (continuous)	Step-Up Dosing Period Index date to end of follow-up. Follow-up will be defined two ways to account for gaps in elranatamab use. See Section 9.7.5 for censoring criteria
4	All-cause pharmacy claims	Pharmacy claim (dichotomous)	

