9.4. Data Sources

This study will be conducted using Komodo Health's Healthcare Map™. The data source is a healthcare technology firm owning, linking, and integrating both open and closed-claims databases from over 150 public and private payers/insurers as well as clearinghouses across the US. The database linkage uses Datavant's encryption and tokenization technology. The data covers more than 330 million individuals including both current (alive) and historical (deceased during the time of study) patients. The database is closely aligned with the National Health Interview Survey population in terms of geography and demographics. This source of insurance claims data encompasses comprehensive, longitudinal records detailing medical procedures, diagnoses, treatments, and associated costs within the healthcare system, as well as patient characteristics and outcomes such as race/ethnicity, zip code, and all-cause mortality records. In this iteration of the Komodo Healthcare Map, only patients with at least one ICD diagnosis code for MM are included in the database.

Mortality records in the data source are obtained from government public records, private claims, and obituaries. For Health Insurance Portability and Accountability Act compliance reasons, mortality is truncated to the year/month of death (YYYY-MM-01). Multiple sources of data are then evaluated, and death dates within 30 days of each other are deduplicated. If multiple sources report different death dates for the same person, then the earlier date is taken.

In order to impute costs, Komodo Heath utilizes the data provided to them by their data sources as well as from as well as publicly available Centers for Medicare & Medicaid Services Medicare fee-for-service pricing tools and methodologies.

This study involved secondary research that utilized de-identified data licensed from a third party, Komodo, in compliance with 45 Code of Federal Regulations 164.514(a)-(c).

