9.7.2. Treatment Exposure Outcomes

Treatment exposure outcomes include RAI and time between administrations. The assessment periods shown in Table 4 are based on the elranatamab label instructions and will be used to measure treatment and dosing-related outcomes for patients receiving elranatamab.¹⁸ These periods are also provided in Figure 2.

[figure not shown]
Table 4. Dosing Schedule and Expected Administrations and Vial Size of Elranatamab

Dosing Schedule	Time Period	Expected Administrations	Vial Size

[figure not shown]
Step-Up	Index date - Day 8	3 during Step-Up	44mg/1.1mL
Maintenance Period 1	Day 9 - Day 168	1 per week	76mg/1.9mL
Maintenance Period 2	Day 169 – Censor	1 every two weeks	76mg/1.9mL

Figure 2. Dosing Schedule for Elranatamab and Teclistamab

Elranatamab label instructions

Teclistamab label instructions

The assessment periods shown in Table 5 are based on the teclistamab label instructions and will be used to measure treatment and dosing-related outcomes for patients receiving teclistamab.¹⁹ These periods are also provided in Figure 2.

Table 5. Dosing Schedule and Expected Administrations and Vial Size of Teclistamab

Dosing Schedule	Time Period	Expected Administrations	Vial Size
Step-Up	Index date - Day 7	3	30 mg/3mL
Maintenance Period	Day 8 - Censor	1 per week	153 mg/1.7mL

Dosing outcomes (reported vial size, average time between claims, and frequency of claims) will be assessed during the above time periods regardless of whether the number of administrations during the period matches the number indicated on the label instructions. Duration on treatment will be measured from the first administration to the last administration of the index drug.

Patients will be censored at the earliest of death, next treatment (CAR-T, BsABs, bendamustine, or belantamab), the end of observability, or the latest data at the time of the specified analysis.

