9.7.4. Time to Discontinuation

TTD will be assessed as the time in months (1 month = 30.4375 days) using Kaplan-Meier methods. Median time-to-event will be reported along with the IQR. The 95% CIs for the median time-to-event will be calculated using log-log transformation. Results will be depicted graphically by Kaplan-Meier curves.

Patients who do not have a recorded discontinuation event or death will be censored on the earliest of the end of continuous closed-claim coverage or the end of data.

The percentage of patients who reached the outcome, as well as the percentage of censored patients, will be reported.

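### OS, TTNT/D and TTD: the end of closed coverage stops only event-free patients, and no sentence limits counted events to the covered period; read literally, this biases the Kaplan-Meier curves downward

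*Protocol*

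**What the plan says.** Protocol section 9.7.7 plans unadjusted Kaplan-Meier estimates of OS and TTNT/D. After defining OS it states: "Patients without an event will be censored at the earliest of the end of continuous closed-claim coverage or the end of data". The TTNT/D sentence has the same form. Section 9.7.4 does likewise for TTD: "Patients who do not have a recorded discontinuation event or death will be censored on the earliest of the end of continuous closed-claim coverage". The data cut-off is the other limit there.

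Section 9.2 stops general follow-up at death, end of data or end of enrollment, but sets these outcomes apart: "Alternative censoring criteria will be applied for certain outcomes (such as OS, TTD, and TTNT/D"), with a pointer to section 9.7. Table 3 gives the OS and TTNT/D assessment period as running from index to censoring and refers to 9.7.7. For TTD it refers to the criteria in 9.7.4.

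On what can be seen after coverage ends, section 9.4 says: "Mortality records in the data source are obtained from government public records, private claims, and obituaries". It describes the vendor as "owning, linking, and integrating both open and closed-claims databases". It also says that "mortality is truncated to the year/month of death (YYYY-MM-01").

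Other outcomes have an unconditional stop. Section 9.7.2, for example, reads: "Patients will be censored at the earliest of death, next treatment (CAR-T, BsABs, bendamustine, or belantamab), the end of observability, or the latest data". Sections 9.7.5 and 9.7.6 are worded in the same way, with coverage end as the limit.

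**The concern.** Kaplan-Meier needs the end of a patient's follow-up to be unrelated to that patient's future event time. Take two patients who both leave closed coverage at month 5. One dies at month 14, and the death appears in public records. The other is alive at month 14. Under the literal rule the first contributes 14 months at risk and an event, and the second is censored at month 5. Among patients who have left coverage, only those who will have an event before the data end remain in the risk set.

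For TTD the route differs but the direction is the same. Table 3 dates the event at the last administration: "Time in months from first administration until last administration prior to treatment discontinuation (continuous"). A death or switch seen after coverage therefore turns a patient censored at coverage end into an event at or before that point. An 8-week gap that appears only because claims are no longer visible could do the same.

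OS and TTNT/D are the study's only effectiveness outcomes (Exploratory Objective 2), and TTD describes treatment duration. The limitations in section 9.9 do not mention the issue.

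**Working it through.** The protocol gives no survival, disenrollment or event figure, so there is no figure of its own to reproduce.

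**Inputs from the protocol.** Indexing starts on 14 August 2023 (section 9.2) and data collection ends on 20 November 2025 (section 6). Maximum follow-up is thus 829 days / 30.4375 = 27.2 months.

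**Assumptions, not in the documents.** Event times T are exponential with median 12, 18 or 24 months. Coverage end C is independent of T, with 10%, 20% or 30% lost per year. Time from index to end of data A is uniform on 0 to 27.2 months. A proportion p of post-coverage events is captured.

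**Direction.** Let S be the survival function and f the density. With full capture, patients past coverage who remain at risk at time t are those with t < T ≤ A. Their hazard is f(t) / [S(t) − S(A)], against a true hazard of f(t) / S(t). The ratio is S(t) / [S(t) − S(A)], which always exceeds 1. For a true median of 18 months, t = 6 and A = 20:
- S(6) = 0.5^(6/18) = 0.794
- S(20) = 0.5^(20/18) = 0.463
- ratio = 0.794 / (0.794 − 0.463) = 2.4

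**Size for a time-to-event outcome dated at the event (OS, TTNT/D).** Kaplan-Meier medians in months, from large simulations (1,000,000 patients per scenario). Literal rule: an event counts at T if T ≤ A and it is captured; otherwise the patient is censored at min(C, A). Capped rule: events and censoring both stop at min(C, A).

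| True median | Annual coverage loss | Capped rule | Literal, p = 25% | Literal, p = 50% | Literal, p = 100% |
|---|---|---|---|---|---|
| 12 | 10% | 12.0 | 11.9 | 11.8 | 11.6 |
| 12 | 20% | 12.1 | 11.8 | 11.7 | 11.3 |
| 12 | 30% | 12.0 | 11.7 | 11.4 | 10.9 |
| 18 | 10% | 18.0 | 17.7 | 17.4 | 17.0 |
| 18 | 20% | 18.0 | 17.5 | 17.0 | 16.1 |
| 18 | 30% | 18.0 | 17.1 | 16.3 | 15.3 |
| 24 | 10% | 24.0 | 23.4 | 22.9 | 22.1 |
| 24 | 20% | 24.1 | 22.9 | 21.9 | 20.5 |
| 24 | 30% | 24.0 | 22.1 | 20.8 | 19.0 |

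Repeat runs differ by about 0.1 month. At full capture, 6% to 20% of counted events fall after coverage ends.

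**TTD.** Further assumptions are a true median of 5 or 8 months, a mean of 10 months from discontinuation to death, and full capture of deaths. A post-coverage death makes a censored patient an event at coverage end. At 10%, 20% and 30% coverage loss, a true 5.0 months becomes 4.9, 4.7 and 4.6, and a true 8.0 becomes 7.7, 7.5 and 7.3. The capped rule returns 5.0 and 8.0. False 8-week gaps are not in these figures and would add to the bias.

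**The alternative of following everyone to the end of data for OS.** With full capture it is unbiased. With a true median of 18 months and 20% annual loss, it gives about 20.1 months at 50% capture and 21.6 at 25%. The literal rule gives about 17.0 and 17.5. Missed post-coverage deaths leave those patients in the risk set as if alive, so the error turns upward and is larger.

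**The case against.** The strongest objection is to the reading. Censoring patients without an event is ordinary Kaplan-Meier wording, and no sentence says that post-coverage events count. Table 3 runs OS and TTNT/D until censoring and ties TTD follow-up to the section 9.7.4 criteria. A programmer could fairly take an event to mean one observed within coverage, and the bias would then vanish. This stands as a limit on the claim, but it does not settle the rule. Table 3 only refers back to the two conditional sentences, section 9.2 takes these outcomes out of the default stop, and section 9.8 commits the analysts to following the protocol strictly.

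The different wording in 9.7.2 and 9.7.5 is weak evidence, because dosing and utilization measures have no terminal event. Section 9.7.6 is more telling: it uses the unconditional form and includes a Kaplan-Meier outcome, time to infection onset.

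The size is wholly assumed, and it is small when survival is short, turnover low or capture poor. Sampling error can also exceed it. At the 56 patients named in section 9.5, with a true median of 18 months and 20% loss, 95% of the simulated medians that are reached lie between about 10.5 and 24 months under either rule. That cohort is expected to grow, however, and a larger cohort does not reduce the bias.

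A reader might also infer that the elranatamab and teclistamab curves are distorted relative to each other. Unequal turnover could do that, but section 9.7 plans no formal comparison and separate reporting by cohort, so no planned inference depends on it.

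**Conclusion.** The point holds as a defect of wording with a definite direction if the text is followed literally: censoring then depends on the future event, and the OS, TTNT/D and TTD curves come out too low. Under 10-30% annual coverage loss and 50-100% capture, a true median of 12 months becomes about 10.9-11.8, 18 becomes 15.3-17.5, and 24 becomes 19.1-22.9. These figures rest on exponential survival, coverage loss independent of outcome, and uniform entry over 27.2 months. None of these is given in the documents.

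Two stronger conclusions are not supported. The protocol does not state that post-coverage events will be counted; it leaves this open. Nor does it establish that deaths are captured equally well after coverage. Section 9.4 lists private claims among the death sources and gives no completeness figure, so following everyone to the end of the mortality data cannot be assumed to be the unbiased choice for OS. The outcomes are exploratory or descriptive, but the correction is cheap and should be made before the final refresh.

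**What to change.** - In 9.7.4 and 9.7.7, end follow-up for all patients at the earliest of the event, the end of continuous closed-claim coverage or the end of data. Count only events on or before that date.
- State how month-truncated death dates are handled at the coverage boundary. A death dated to the first of the month can appear to precede a coverage end that it actually followed. If enrollment closes because of the death, a short stated allowance may be needed.
- For TTD, require the 8-week gap to lie fully within coverage. Do not let a death or switch seen after coverage turn a censored patient into an event.
- For OS, report follow-up of all patients to the end of the mortality data, regardless of coverage, as a sensitivity analysis only.
- Report how many deaths and switches fall after coverage ends, so that readers can judge the size in these data.

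The cost is a few sentences and a date filter, with no new data. A few post-coverage events are dropped, so precision falls slightly. The capped rule still assumes that leaving coverage is unrelated to prognosis, which section 9.9 should state.

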9.8. Quality Control

Redacted will code measures for cohort identification, outcomes, and other variables of interest based on codes and algorithms described in this protocol. This protocol will be strictly followed when conducting the analysis of this study. All cohorts developed, statistical

analyses implemented, and tables completed will undergo quality control review by at least one additional analyst or scientist under the supervision of the Study Lead. The Study Lead will review all results tables and other final deliverables to confirm accuracy, logical flow, and appropriate format.

9.9. Limitations of the Research Methods

While claims databases provide a wealth of comprehensive information to assess patients' demographic and clinical characteristics, a few limitations arise when using such databases. For instance, there may be misclassification of patient records due to provider coding practices (eg, using a diagnosis code as a rule-out criterion) or incorrect coding (eg, data entry errors). As such, the presence of a diagnosis code may not always accurately reflect the presence of disease for an individual patient. Such errors could affect patient eligibility and all variables used to assess treatment characteristics, HCRU, etc. Another potential issue that arises when using any database is generalizability. Oftentimes, the demographic makeup of the dataset is dependent on the providers that supply the information; if a dataset is heavily receiving data from one region of the US, then that might affect overall generalizability.

Databases that contain open and closed claims can offer information in real-time; they often are large in size and have a quick update cadence that allows for the immediate analysis of patient data. However, despite these strengths, there are some limitations associated with the use of open and closed claims. There is a risk of both patient and claim duplication, i.e., where the same patient shows up with a unique patient ID multiple times within the data. With a small cohort size, it may be hard to ascertain if such patients are unique to the dataset or if they are duplicates. Additionally, data providers such as Komodo are beholden to the suppliers of their claims data; therefore, if a data supplier withdraws and no replacement is found, then patient counts could drop across cuts.

Clinical events of interest defined by diagnosis codes may not capture the occurrence or intensity of the disease. Certain conditions, such as hematological toxicities, are often defined via specific cut-offs for certain lab values, which are not often provided in a claims data source. Therefore, ICD codes are used instead. Without lab values, the severity of the disease/grade cannot be determined. Therefore, patients whose AEs were not as severe in grade may not be captured.

Claims data such as Komodo Health do not contain variables used to assess standard oncology endpoints. Claims databases do not often detail clinical contexts, such as physician notes, imaging results, or laboratory findings. Common oncology endpoints such as real-world progression-free survival, real-world objective response rate, and reasons for discontinuation are typically defined using variables abstracted from patient charts that are not available in a claims dataset.

The recency of elranatamab approval is important for interpreting results. The expected sample size is low, potentially resulting in uncertain estimates, as evidenced by wide CIs. Very few eligibility criteria will be applied, which may allow patients with other malignancies or other conditions that are often excluded in a real-world study to enter.

Additionally, the patients who have received elranatamab soon after approval may have more severe or advanced disease. Due to the recency of elranatamab approval, the generalizability of outcomes may be limited to a short period following initiation.

9.10. Other Aspects

Not applicable.

10. PROTECTION OF HUMAN PARTICIPANTS

10.1. Patient Information

This study involves data that exist in deidentified/anonymized structured format and contain no patient personal information.

10.2. Patient Consent

As this study involves deidentified/anonymized structured data, which according to applicable legal requirements do not contain data subject to privacy laws, obtaining informed consent from patients by Pfizer is not required.

10.3. Institutional Review Board (IRB)/ Ethics Committee (EC)

This study does not require IRB/EC approval. An exemption was received.

10.4. Ethical Conduct of the Study

The study will be conducted in accordance with legal and regulatory requirements, as well as with scientific purpose, value, and rigor and follow generally accepted research practices described in Guidelines for Good Epidemiologic Practice practices laid out in 2005 FDA Good Pharmacoepidemiology Practices (GPP),²⁰ Best Practices for Conducting and Reporting Pharmacoepidemiologic Safety Studies Using Electronic Healthcare Data Sets,²¹ and the 2015 International Society of Pharmacoepidemiology GPP.²²

